9.2 Transformation of weekly e-Diary data

Subjects will be asked to fill in the weekly e-Diary every week from visit 1 to end-of-trial visit. Every week between Sunday 8 pm and Tuesday 2 am the subject should answer the following question:

Instructions and the question to be answered are:

During the last week, because of your endometriosis, how often have you...

	Never	Rarely	Sometimes	Often	Always
1. Been unable to go to social events because of the pain?					
2. Been unable to do jobs around the house because of the pain?					
3. Found it difficult to stand because of the pain?					
4. Found it difficult to sit because of the pain?					
5. Found it difficult to walk because of the pain?					
6. Found it difficult to exercise or do the leisure activities you would like to do because of the pain?					
7. Lost your appetite and/or been unable to eat because of the pain?					
8. Been unable to sleep properly because of the pain?					
9. Had to go to bed/lie down because of the pain?					
10. Been unable to do the things you want because of the pain?					
11. Felt unable to cope with the pain?					
12. Been unable to do jobs around the house, at work, or at school because of the pain?					

The additional work item (Question 12) will only be used for validation of the weekly e-Diary. The secondary endpoint of changes in the weekly pain impact scores will be based on the original EHP-30 pain impact domain, i.e. the first 11 items.

The weekly EHP-30 pain impact score will be calculated based on question 1 to 11 in the following way, a raw score will be calculated as the sum of scores from each question were an answer of never will be scored as 0, rarely as 1, sometimes as 2, often as 3, and always as 4. This raw score will then be multiplied with 100 and divided by 44, (So that the score will be between 0 and 100, 0 indicating the best health status and 100 the worst health status).

The weekly EHP-30 pain impact score will assigned to cycles in the following way. The week mentioned in the questionnaire as last week will be regarded as the week starting on a Monday and ending on the Sunday where the questionnaire is opened for access, both days included. The weekly score will be assigned to the cycle that cover most of that week. So if the first day of the current cycle (the cycle that includes the Sunday where the questionnaire is opened for access) is on the Thursday of that week or before the week will be assigned to the current cycle. If the first day of the current cycle is on the Friday of that week or later the week will be assigned to the previous cycle.

The mean weekly score is calculated as a simple mean of the weekly scores assigned to that cycle. The mean weekly scores will be calculated as long at least one weekly score is not missing. The baseline weekly score is the average of the two mean weekly scores from cycle -2 and cycle -1.

9.3 General Considerations

All efficacy endpoints will be summarised by treatment using descriptive statistics. Categorical data will be summarised using numbers and percentages (n and % of all observed) in addition to the sum 'All', the percentages are based on the total number of subjects with a corresponding assessment in the analysis set. Continuous data will be presented, using the number of subjects (n), mean and standard deviation, median, 25th percentile, 75th percentile, minimum, and maximum. The primary endpoint will be summarized using both the ITT population and the PP population, all other endpoints will be summarized using only the ITT population.

As the trial has been prematurely discontinued, it has been decided, due to the low number of subjects, that no statistical analysis will be performed, see section 1 and 12.

9.3.1 Efficacy and exploratory endpoints

For the primary endpoint, each of the secondary, and each of the exploratory endpoints mentioned in Table 9-1 the absolute value at baseline and the absolute value at cycle 1 to 4 (if appropriate), and the change from baseline at cycles 1 to 4 (if appropriate) will be summarised by treatment.

Table 9-1 Efficacy and Exploratory Endpoints

Endpoint
Changes in the mean daily NRS scores for the worst endometriosis-related pain at cycle 4
Changes in the mean daily NRS scores for the worst endometriosis-related pain over 8 menstrual cycles
Changes in the mean daily NRS scores for the worst dysmenorrhea and for the worst non-menstrual pelvic
pain over 8 menstrual cycles
Changes in the mean daily NRS scores for the worst dyspareunia on days with sexual intercourse over
8 menstrual cycles
Frequency of avoiding sexual intercourse due to expected pain over 8 menstrual cycles
Changes in the mean daily NRS scores for the worst impact of endometriosis-related pain on the subject's
ability to function over 8 menstrual cycles
Changes in the mean weekly scores of the EHP-30 pain impact domain over 8 menstrual cycles
Changes in vaginal bleeding pattern over 8 menstrual cycles
Percentage of days with mild and/or strong rescue analgesics used over 8 menstrual cycles
Total and average doses of mild and/or strong rescue analgesics used over 8 menstrual cycles
Responder rate assessed as ≥30%, ≥50% and ≥70% reduction from the baseline in mean daily NRS scores
for the worst endometriosis-related pain, dysmenorrhea, non-menstrual pelvic pain and for the worst
endometriosis-related pain impact over 8 menstrual cycles
Changes in the mean individual and total symptom and sign severity scores of the B&B scale at cycles 4
and 8
Changes in EHP-30 scores over 8 menstrual cycles
Changes in PGIS scores at cycles 4 and 8
PGIC scores at cycles 4 and 8
Serum levels of mid-luteal phase progesterone ^f , estradiol, prolactin, TSH and IGF-1 at cycles 4

9.4 Analysis of Pharmacokinetics

The pharmacokinetic data will be reported elsewhere.

10 Safety

10.1 General Considerations

Safety parameters will be evaluated for the safety analysis data set.

All safety summaries will be performed by treatment:

For adverse events (AE) and concomitant medications the following rules will apply;

Treatment period	AE and concomitant medications to be included
Part A	Start after start of IMP, and start date before or equal to the date of the end-of-cycle 4 visit, if missing use date of premature discontinuation
Part B	Start date after the date of the end-of-cycle 4visit and before or equal to date last ring removal, if missing use date of premature discontinuation.

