- 16. History of orthostatic hypotension or recurrent syncope.
- 17. History of mental illness including occurrence of acute psychosis, bipolar disorders and schizophrenia (except for well-controlled anxiety and/or depression with no changes to interventions for 6 months prior to start of run-in).
- 18. History of impulse control disorders including pathological gambling, compulsive buying, hypersexuality, and binge eating or being identified with potential impulse control disorder by the questionnaire for impulsive-compulsive disorders (a score ≥2 for any sub-questions of Question 3 or a score ≥1 for any sub-questions of Question 4) prior to randomization.
- 19. History of valvular heart disease.
- 20. History of sudden sleep onset episodes.
- 21. Any clinically significant abnormal findings from vital signs, urinalysis, blood tests of hematology and clinical chemistry at screening, including a drop of 20 mmHg of systolic blood pressure or a drop of 10 mmHg of diastolic blood pressure within three minutes of standing from a sitting position, alanine aminotransferase (ALT) >2.5 times upper limit of normal (ULN) or bilirubin >1.5 times ULN or creatinine >1.5 mg/dL.
- 22. Any clinically significant abnormal findings from blood test of endocrine parameters (including signs indicating menopausal status but excluding hyperprolactinemia) at screening.
- 23. Any clinically significant abnormal findings from physical examination at screening.
- 24. Any vaginal or vulvar lesions that could interfere with vaginal ring usage.
- 25. Any significant abnormal ECG or echocardiography findings (e.g. valvular regurgitation or stenosis) before randomization.
- 26. Any recent suicidal ideation of type 4 (i.e. active suicidal ideation with some intent to act, without specific plan) or type 5 (i.e. active suicidal ideation with specific plan and intent), or any recent suicidal behavior identified by the electronic Columbia-Suicide Severity Rating Scale at screening.
- 27. Hypersensitivity to any active ingredient, excipients or other component of medicinal products used in the trial, including quinagolide vaginal ring, placebo vaginal ring and ibuprofen.
- 28. Known serious adverse drug reactions to dopamine agonist.
- 29. Current or history of gastrointestinal ulcer or gastrointestinal bleeding within 6 months of the run-in visit.

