		10.5.3	Impulsiv	e-Compulsive Disorders	41
		10.5.4	Ring Acc	ceptability	41

Statistical Analysis Plan	Version: 1.0	FERRIN	
Quinagolide	31MAY2022	PHARMACEUT	
FE 999051 trial 000165	CONFIDENTIAL	Page 4	

11	Interim Analyses	+ ∠
12	Deviations from Protocol Analysis	43

1 Introduction

This document describes the planned statistical analyses for trial 000165, and is based on versions 4.0, 5.0, and 6.0 of the clinical trial protocol dated 9th of July 2018, 27th of March 2019, and 29th of May 2020.

During this trial subjects were randomized under three consecutive versions of the protocol; version 4.0, version 5.0, and version 6.0. As the majority of subjects were randomized under protocol version 5.0, this will be used as the basis for the clinical trial report.

These protocol amendments included modifications to the eligibility criteria, modifications to the overall trial design, and changes to reflect the impact of the COVID-19 pandemic on the conduct of the trial. The change in trial design was in protocol version 6.0, the quinagolide extended-release vaginal rings were administered sequentially for 4 menstrual cycles instead of 8 menstrual cycles. Therefore, in version 6 subjects completed treatment Part A (cycles 1 to 4) only, there was no treatment Part B (cycles 5 to 8), and the follow-up period was for one menstrual cycle only (cycle 5).

The trial was terminated early. The decision was taken due to the results from the parallel phase 2 trial in Europe (Trial 000295) and the continued difficulties with subject recruitment.

Furthermore, due to the low number of subjects recruited, no interim analysis will be performed, and no statistical analysis will be performed. Instead results are presented as descriptive statistics by treatment group separately for Part A and Part B. In this SAP when results are summarized by treatment it means two tables one for Part A (with 4 treatments, Placebo and the 3 doses of quinagolide) and one for Part B (with 6 treatments, Placebo followed by each of the 3 doses of Quinagolide and continued use of each of the 3 doses of quinagolide).

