7.3 Prior and Concomitant Medication

Prior and concomitant medication will be summarised by ATC classification 1st level (alphabetically), ATC classification 2nd level (in decreasing order of frequency) and treatment group. These medications will be tabulated separately for:

- 1) Prior medication; i.e. medication taken exclusively prior to treatment (i.e. with stop date before date of first ring insertion);
- 2) Concomitant medication, i.e. medication taken during the treatment period (i.e. medication that was not stopped before date of first ring insertion and not started after the last ring removal.
- 3) Post-treatment medications, i.e. medications starting after the treatment period (i.e. with start after the last IMP removal).

The number of subjects with "any medication" will be included in these tables. If the timing of the dose of a concomitant medication cannot be established in relation to the administration of IMP, it will be considered as concomitant medication.

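### SAP 10.1 assigns concomitant medications to Part A or Part B by start date alone, which conflicts with the overlap definition in SAP 7.3, and the SAP does not say which prevails

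*SAP*

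**What the plan says.** **Definition.** SAP 7.3 sorts medications into three tables. Prior medication stopped before the first ring was inserted. Post-treatment medication began after the last ring was removed. Concomitant medication is "medication that was not stopped before date of first ring insertion and not started after the last ring removal". Where "If the timing of the dose of a concomitant medication cannot be established in relation to the administration of IMP", the medication counts as concomitant.

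**Assignment to a part.** SAP 10.1 opens its inclusion table with "For adverse events (AE) and concomitant medications the following rules will apply". The Part A row is "Start after start of IMP, and start date before or equal to the date of the end-of-cycle 4 visit". The Part B row is "Start date after the date of the end-of-cycle 4visit and before or equal to date last ring removal". Both rows fall back on the date of premature discontinuation when the closing date is missing.

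**Layout.** SAP 7 presents its summaries by treatment with a total column. SAP 1 explains what that means: "In this SAP when results are summarized by treatment it means two tables one for Part A" and one for Part B.

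**Listing.** SAP 7.5 lists all medications, including start date and ATC level, with no restriction by part.

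**The concern.** A start-date rule suits adverse events, where the question is what newly arose in each part. It does not suit medication, where the question is what the woman was taking. The two rules therefore give different answers for any drug already in use when a part begins.

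The protocol expects such drugs. Section 4.1.2 admits women with "well-controlled anxiety and/or depression with no changes to interventions for 6 months prior to start of run-in", and section 7.4.17 collects medication use from three months before consent. If a permitted anxiety or depression intervention is a drug and has not been changed, it began before the first ring. Under the 10.1 rows it would be counted in neither part, so the tables would suggest that no one took it. The trial now reports descriptive statistics only, so the summary tables should be correct on their own terms.

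**Working it through.** The plan gives no figure to reproduce. The check is to pass medication histories through both rules.

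**Inputs.** The 7.3 definition and the two 10.1 rows, as quoted above. The days are illustrative assumptions: first insertion on day 0, end-of-cycle 4 visit on day 112, last ring removal on day 224. The classification depends only on the order of the dates, not on these values.

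**Rules**, with s = start day and e = stop day:
- 7.3: prior if e < 0; post-treatment if s > 224; otherwise concomitant.
- 10.1 Part A: 0 < s ≤ 112.
- 10.1 Part B: 112 < s ≤ 224.
- Actually taken in Part A: s ≤ 112 and e ≥ 0.
- Actually taken in Part B: s ≤ 224 and e > 112.

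| History (s, e) | 7.3 | 10.1 places it in | Taken in |
|---|---|---|---|
| Stopped before insertion (−60, −10) | prior | neither | neither |
| Started before, ongoing throughout (−200, none) | concomitant | neither | A and B |
| Started before, stopped in A (−200, 50) | concomitant | neither | A |
| Started before, stopped in B (−200, 150) | concomitant | neither | A and B |
| Started and stopped in A (20, 60) | concomitant | A | A |
| Started in A, stopped in B (20, 180) | concomitant | A | A and B |
| Started in B (130, 150) | concomitant | B | B |
| Started on insertion day (0, 60) | concomitant | neither, if dates alone are compared | A |
| Started after last removal (230, 240) | post-treatment | neither | neither |

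**Reading the table.**
1. The three histories that start before insertion and run past it are concomitant under 7.3 and fail both 10.1 rows. They are not prior, because they did not stop, and not post-treatment, because they did not start late. If 10.1 governs, they enter no summary table.
2. The history that starts in Part A and runs into Part B is shown in Part A only.
3. The rules agree for a drug that starts and stops in Part A, or that starts in Part B.
4. The 7.3 provision for unclear timing does not help, because the start of these drugs is known to precede the ring.

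**Does another passage settle it?** SAP 7.3 has no boundary at the end-of-cycle 4 visit, so it cannot by itself produce the Part A and Part B tables that SAP 1 requires. SAP 10.1 has that boundary. SAP 10.2 to 10.5 plan no medication table of their own, so the only tables to which the 10.1 medication rule could apply are those of 7.3.

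**The case against.** The strongest reply is that the medication tables belong to 7.3, which states its own inclusive rule. Section 7 uses the ITT set by default, while 10.1 is a general paragraph for safety summaries on the safety set. Nothing says that 10.1 overrides 7.3, and a programmer who follows 7.3 keeps ongoing drugs. This stands in part: the omission is conditional on 10.1 being applied. It does not remove the conflict, because 10.1 names concomitant medications and is the only rule that assigns them to a part.

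Three stronger readings are tempting, and the documents do not support them.
- *These tables are the only view of background treatment, so an imbalance between arms could not be seen.* The SAP 7.5 listing keeps every medication. SAP 7.2 reports ongoing medical history separately by system organ class and preferred term, so ongoing anxiety or depression would appear by arm as a condition, though not as a drug. An imbalance would be harder to see, not hidden.
- *Treatments that affect pain would go uncounted.* Rescue analgesics come from the e-Diary and are derived under SAP 9.1.5 and summarised under 9.3.1. Protocol 4.3.1 prohibits hormonal treatments, dopamine agonists, COX2 inhibitors and long-acting narcotics. Protocol 4.1.2 excludes conditions that need continuous analgesics.
- *Cancelling the adjusted analysis removed protection against such an imbalance.* The model in protocol 9.6.2 adjusted for baseline pain score and baseline percentage of days on rescue analgesics. It never adjusted for other medication.

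**Conclusion.** The conflict between SAP 7.3 and SAP 10.1 is real, and the SAP leaves precedence unstated. If 10.1 is applied to the by-part tables, all medication with a known start before the first ring that continued past insertion is absent from the summaries, and medication carried from Part A into Part B is absent from Part B. How many records this affects cannot be stated, because the documents give no medication counts.

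The error is minor. It concerns descriptive medication tables in a trial that stopped early and has no planned inference. The primary endpoint and the adverse event tables do not depend on it. The conclusion assumes that the 10.1 rule is meant for the 7.3 tables, which is the only use the SAP leaves for it.

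**What to change.** Limit the 10.1 start-date table to adverse events, and state in 7.3 that medications are split by overlap:
- **Part A:** not stopped before first ring insertion, and started on or before the end-of-cycle 4 visit or, if that visit is missing, the date of premature discontinuation.
- **Part B, only for women who entered it:** ongoing or stopped after the end-of-cycle 4 visit, and started on or before the last ring removal or, if that date is missing, the date of premature discontinuation.
- A medication that spans both parts appears in both tables.
- The 7.3 rule that unclear timing counts as concomitant is kept, as are its prior and post-treatment categories.

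Applied to the histories above, a drug ongoing throughout enters both tables, one started before the ring and stopped in Part A enters Part A only, and one started in Part A and continued enters both. The cost is a change of SAP wording and one revised selection rule in the table program. No new data are needed.

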#### Urinalysis

Urinalysis parameters will be summarized descriptively.

<sup>g A treatment-emergent adverse event is any adverse event occurring after start of IMP and before the end-of-trial visit, or a pre-treatment adverse event or pre-existing medical condition that worsens in intensity after start of IMP and before the end-of-trial visit.

<sup>h A pre-treatment adverse event is any adverse event occurring after signed informed consent and before start of IMP or a pre-existing condition that worsens in intensity after signed informed consent but before start of IMP.

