2.6 Exploratory Endpoint

Changes in endometriosis biomarkers such as serum levels of VEGF, placenta growth factor (PlGF), interleukin 6 (IL-6) and soluble fms-like tyrosine kinase 1 (sFlt-1) at cycles 4 and 8.

3 Trial design

This is a randomized, double-blind, placebo-controlled, phase 2 trial assessing the efficacy, safety and dose-response of quinagolide extended-release vaginal rings administered sequentially for 4 menstrual cycles in women with moderate to severe endometriosis-related pain. In this trial, a menstrual cycle is considered the period from day 7 of return of menses (RM+7) in a cycle until the following day 7 of return of menses in the next cycle. Visits on RM+7 can be scheduled on RM+6-10, i.e. day 6 to day 10 of return of menses.

The trial consists of the following periods:

- 1) Screening: starting immediately after the signing of the informed consent(s) and including a run-in period of two complete menstrual cycles (cycles -2 and -1)
- 2) Part A: double-blind, placebo-controlled treatment with three doses of quinagolide extended-release vaginal ring administered sequentially for four menstrual cycles (cycles 1, 2, 3 and 4)
- 3) Part B: double-blind, extension treatment with three doses of quinagolide extendedrelease vaginal ring administered sequentially for four menstrual cycles (cycles 5, 6, 7 and 8)
- 4) Follow-up: post-treatment follow-up period of two menstrual cycles (cycles 9 and 10)

Statistical Analysis Plan	Version: 1.0	FERRING
Quinagolide	31MAY2022	PHARMACEUTICALS
FE 999051 trial 000165	CONFIDENTIAL	Page 11 (44)

Abbreviations: B&B=Biberoglu and Behrman Scale, BTM=bone turnover markers, E2=estradiol, Echo=echocardiography, ECG=electrocardiography, EHP-30=Endometriosis Health Profile-30 Questionnaire, LH=luteinizing hormone, LH+7=7 days after LH surge, NRS=Numerical Rating Scale, P4=progesterone, PGIC=Patient Global Impression of Change, PGIS=Patient Global Impression of Severity, PG=pharmacogenetic(s), PK=pharmacokinetic(s), QICD=questionnaire for impulsive-compulsive disorders, QVR=quinagolide vaginal ring, RM=return of menses, RM+7=day 7 of return of menses, TVU=transvaginal ultrasound

- In case of technical issues at the start of the run-in period, subjects are allowed to re-start e-Diary recording for cycle -2. а

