10.2 Adverse Events

AEs are classified according to MedDRA version 20.0.

Written narratives will be issued for all serious AEs (including deaths) and AEs leading to withdrawal.

A pre-treatment adverse event is any adverse event occurring after signed informed consent and before start of IMP or a pre-existing condition that worsens in intensity after signed informed consent but before start of IMP. Pre-treatment AEs will be presented in a separate data listing only.

A treatment-emergent adverse event (TEAE) is any adverse event occurring after start of IMP and before the end-of-trial visit, or a pre-treatment adverse event or pre-existing medical condition that worsens in intensity after start of IMP and before the end-of-trial visit.

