10.2.3 Incidence of Adverse Events of Special Interest

10.2.3.1 Dizziness/Pre-syncope

Treatment-emergent adverse events of dizziness/pre-syncope will be summarised, similar to the tables described in 10.2.2. Two tables will be prepared one with all TEAE and one with related TEAE(as assessed by the investigator). An AE is considered to be dizziness/pre-syncope if the PT is included in the list below:

Dizziness Dizziness postural Dizziness exertional Persistent postural-perceptual dizziness Procedural dizziness Pre-syncope Vertigo Vertigo positional Vertigo CNS origin

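### SAP 10.1's adverse-event windows close before the end point in SAP 10.2's definition of a treatment-emergent event; applied as written, they leave events starting in follow-up out of the TEAE tables

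*SAP*

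**What the plan says.** - **Allocation windows.** SAP 10.1 states that all safety summaries are by treatment and gives two inclusion rules for adverse events. Part A: "Start after start of IMP, and start date before or equal to the date of the end-of-cycle 4 visit". Part B: "Start date after the date of the end-of-cycle 4visit and before or equal to date last ring removal". In each row the date of premature discontinuation replaces a missing closing date. There is no row for follow-up.
- **Tables available.** SAP section 1 fixes the meaning of the phrase: "when results are summarized by treatment it means two tables one for Part A", and the other is for Part B.
- **Definition.** SAP 10.2 defines a TEAE as "any adverse event occurring after start of IMP and before the end-of-trial visit", together with earlier conditions that worsen in that interval. Protocol version 6.0, section 9.8, footnote g, has the same end point: "A treatment-emergent adverse event is any adverse event occurring after start of IMP and before the end-of-trial visit".
- **Planned output.** The first category in both SAP 10.2.1 and SAP 10.2.2 is all TEAEs. The special-interest tables are built the same way, for example: "Treatment-emergent adverse events of dizziness/pre-syncope will be summarised, similar to the tables described in 10.2.2".
- **Follow-up.** It lasts one cycle (cycle 5) under version 6.0 (SAP section 1) and two cycles (9 and 10) in the 8-cycle design (SAP section 3).
- **Declared changes.** SAP section 12 lists the dropped interim and statistical analyses, shift tables, markedly-abnormal tables, progesterone proportion and biomarker summaries. It does not mention a restriction on the adverse-event tables.

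**The concern.** The definition and the allocation rule cover different time spans. An event that starts after the window closes and before the end-of-trial visit meets the definition but has no table to enter.

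No statistical analysis will be done, so the descriptive TEAE tables are a main safety output. Their counts and percentages could be lower than the SAP's own definition gives. A serious event starting in follow-up could be listed and narrated yet be absent from the serious-TEAE table. Protocol 8.5.1 asks for full documentation of deaths within four weeks after treatment ends, so the interval is one in which the sponsor expects to report events.

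**Working it through.** The plan gives no figure to reproduce. The check sets the rules side by side and then measures the interval between them.

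**Step 1: the rules together**

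| Subject | Last day with a table (SAP 10.1) | Last day of TEAE status (SAP 10.2) |
|---|---|---|
| Version 6.0 completer | End-of-cycle 4 visit | Day before the end-of-trial visit, end of cycle 5 |
| 8-cycle completer | Last ring removal, end of cycle 8 | Day before the end-of-trial visit, end of cycle 10 |
| Early discontinuer | Date of premature discontinuation | Day before the end-of-trial visit |

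Part B cannot catch the version 6.0 events. Protocol 6.4.6 has the last ring removed at the end-of-cycle 4 visit, so the Part B window is empty for these subjects.

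**Step 2: length of the uncovered interval, constant cycles**

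Assume cycle length L of 24, 28 or 35 days. The range comes from inclusion criterion 11, which covers only the run-in cycles, so its use here is an assumption. Count days from first ring insertion.

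- Version 6.0 completer: uncovered days = 5L − 4L − 1 = L − 1, out of 5L − 1 TEAE days. Results: 23 of 119, 27 of 139 and 34 of 174, or 19.3% to 19.5%.
- 8-cycle completer: uncovered days = 10L − 8L − 1 = 2L − 1, out of 10L − 1. Results: 47 of 239, 55 of 279 and 69 of 349, or 19.7% to 19.8%.

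**Step 3: allowing for the visit window**

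Visits fall on day 6 to 10 of menses (protocol 6.1; SAP section 3). Two visits n cycles apart are therefore nL − 4 to nL + 4 days apart, and the uncovered days number nL − 5 to nL + 3.

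- n = 1 (version 6.0): 24 − 5 = 19 up to 35 + 3 = 38 days.
- n = 2 (8-cycle): 48 − 5 = 43 up to 70 + 3 = 73 days.

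**Step 4: early discontinuers under version 6.0**

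Assume the discontinuation date is the last ring removal and the end-of-treatment visit follows within the preferred 7 days (protocol 3.6.7).

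- After an adverse event, the end-of-trial visit is within 2 weeks of the end-of-treatment visit (protocol 6.1.1): 0 to 7 + 14 − 1 = 20 days.
- For other reasons, with both visits coinciding: 0 to 7 − 1 = 6 days.
- If the discontinuation date is instead the end-of-treatment visit, the first interval is at most 14 − 1 = 13 days.

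**Step 5: a case the protocol permits**

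Under version 6.0 the end-of-treatment echocardiogram may be done up to 2 weeks after visit 10 (protocol 7.2.2.9). A clinically significant finding is an adverse event (protocol 8.1), and its onset is the examination date (protocol 8.2.2). Visits 10 and 11 are at least 24 − 4 = 20 days apart under the assumptions above. An echocardiogram 1 to 14 days after visit 10 therefore precedes visit 11, and the resulting event is a TEAE outside both windows. The finding itself still counts in the SAP 10.5.2 proportion.

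**The case against.** The strongest reply is that 10.1 is deliberate. Its windows sit under a column headed as treatment period and carry explicit dates, so a careful reader can see an on-treatment display. That much stands. But 10.2 has no on-treatment definition, and 10.2.1 and 10.2.2 still call for all TEAEs. Nor does the SAP confine other safety data to treatment: SAP 10.3.1 and 10.4.1.1 summarise laboratory and vital-sign changes at end of trial.

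A second reply is that the words all TEAEs might govern, in which case follow-up events would be counted. The SAP does not say which rule prevails. The supportable claim is therefore a conflict between two sections, with omission following if 10.1 is applied as written. A reader might infer that omission is certain; the text does not go that far.

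Three other inferences also go too far:

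- **That safety events are lost.** They are not. SAP 10.2.2 lists all adverse events, and SAP 10.2 requires narratives for serious events and those leading to withdrawal.
- **That the SAP departs from the governing protocol without saying so.** SAP section 1 makes version 5.0 the basis of the report, and that text is not available. Non-declaration in section 12 can be shown only against version 6.0.
- **That about a fifth of events go uncounted.** The 19% to 20% is a share of days, and those days are drug-free. Protocol 1.3 reports that most events in the single-ring phase 1 trial began in the first week, and that reactions to oral tablets occur mainly in the first few days.

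The echocardiogram example is also narrow. In the 8-cycle design, a late cycle-4 echocardiogram in a subject continuing into Part B falls inside the Part B window.

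**Conclusion.** SAP 10.1 and SAP 10.2 conflict. If 10.1 is followed literally, events starting in post-treatment follow-up are TEAEs by definition but are not counted in the overview, incidence or special-interest tables.

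The uncovered time is about one cycle per version 6.0 completer and two per 8-cycle completer, and shorter or absent for version 6.0 subjects who stop early. These lengths rest on 24- to 35-day cycles continuing after run-in and, for early discontinuers, on what the discontinuation date means. The internal conflict itself needs no assumption.

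The number of affected events is unknown and may be small. No efficacy result or test is touched. The point ranks between minor and should-fix: a stated rule gives counts that disagree with the SAP's own definition, while the listings remain complete.

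**What to change.** In SAP 10.1, add a follow-up period that starts the day after the subject's Part A or Part B window closes and runs to the end-of-trial visit. Starting it from the window's closing date, rather than from ring removal, avoids counting an event twice when the discontinuation date is later than ring removal. Show it as a separate follow-up table or set of columns by treatment group within the overview, incidence and special-interest output. State how events are attributed, for example to the last treatment received, and reconcile that with SAP 6.3, which assigns a subject who received more than one treatment to the highest quinagolide dose.

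If an on-treatment restriction is intended, change the 10.2 definition and the table titles to on-treatment, and declare the departure from protocol version 6.0 in section 12.

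The cost is SAP wording, one period flag and one additional set of adverse-event tables or columns. A single extra column would not be enough, because there are four treatment groups in Part A and six in Part B. No new data are needed: protocol 7.2.2.11 already records adverse events until the end-of-trial visit.
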